2.7.1 Sample size

It was a priori determined, based on the reduction of ESS, that a sample size of 100 patients per group (200 patients total) was required for a power of 90%, assuming for a non-inferiority margin of 2.0 and a standard deviation of ESS changes of 2.0. The one-sided significance level (alpha) of the test was set at 0.025.

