2.7 Statistical analysis

Statistical analysis for primary and secondary clinical end points will compare changes in scores at 3 months and six months between groups, using ANOVA. The lower limit of the two-sided 95% confidence intervals will be used to determine noninferiority. We anticipated an equal drop out rate (10 %) in the two study arms. All analyses were conducted in an intention-to-treat manner.

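### The 100 patients per group said to be required for 90% power do not follow from the stated inputs, which need 23 per group if the true difference is zero

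*Combined protocol and SAP*

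**What the plan says.** Section 2.7.1 bases the sample size on the reduction in Epworth Sleepiness Scale (ESS) score. It states that "a sample size of 100 patients per group (200 patients total) was required for a power of 90" per cent, "assuming for a non-inferiority margin of 2.0 and a standard deviation of ESS changes of 2.0". It adds: "The one-sided significance level (alpha) of the test was set at 0.025". It gives no assumed true difference between the arms and does not say whether the 100 already allows for dropout.

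Section 2.7 states: "We anticipated an equal drop out rate (10 %) in the two study arms". The analysis will "compare changes in scores at 3 months and six months between groups, using ANOVA". The decision rule there is: "The lower limit of the two-sided 95% confidence intervals will be used to determine noninferiority". The rule names no value against which the limit is to be compared.

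Section 2.3 gives 1:1 allocation and a randomisation list for 200 patients. Section 2.5 gives minimal important differences for the five quality-of-life domains but none for ESS.

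**The concern.** A margin equal to one standard deviation is a wide margin in statistical terms, and a two-arm comparison of means against it needs only a few dozen patients in total. A requirement of 200 for 90% power is therefore out of scale with the inputs printed beside it.

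More patients than necessary would not harm the ESS comparison. The difficulty is that this sentence is the only place where the ESS non-inferiority margin appears. If its numbers do not agree, a reader cannot tell which of them the trial was designed on, and the possible explanations have different consequences:

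- If the margin used was nearer 1, the printed threshold is about twice the one the trial was sized for, and a result that fails the intended margin could be declared non-inferior.
- If the SD used was a little above 4, the trial has about 90% power and no large reserve.
- If a true deficit in the nurse arm was assumed, the design planned for a worse nurse arm without saying so, and the required size depends heavily on that assumption.

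**Working it through.** **Inputs.** Margin M = 2.0, SD of ESS change = 2.0, one-sided alpha = 0.025 and power = 90% (section 2.7.1); 1:1 allocation (section 2.3); dropout 10% per arm (section 2.7). The true nurse-arm deficit d is not stated and is set to zero as an assumption, then varied.

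**Attempt to reproduce the stated 100.** The normal approximation is

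n per group = 2 × (z₀.₉₇₅ + z₀.₉₀)² × (SD / (M − d))²

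= 2 × (1.960 + 1.2816)² × (2.0/2.0)² = 21.01, rounded up to 22. With dropout, 22/0.9 = 24.4, so 25.

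The exact calculation (noncentral t, 2n − 2 degrees of freedom) gives power 0.8997 at n = 22 and 0.9125 at n = 23, so 23 are needed. With dropout, 23/0.9 = 25.6, so 26.

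The stated figure is not reproduced: 100/23 = 4.3. If 100 is the number before dropout, 90 are evaluable, and 90/23 = 3.9.

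**Power at the stated size** (M = 2.0, SD = 2.0, d = 0, exact t): 1 − 1.2×10⁻⁶ at 90 per group and 1 − 1.9×10⁻⁷ at 100 per group.

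**Could another feature of the design explain the gap?** With margin and SD as printed and d = 0 (exact t unless noted):

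| Variant | n per group |
|---|---|
| Alpha halved to 0.0125 for two visits | 27 (30 after dropout) |
| Success at both visits, power √0.9 at each, independence assumed | 27 (30 after dropout) |
| Alpha divided by 6 (ESS and five quality-of-life domains) | 33 |
| Alpha divided by 12 (the same at two visits) | 37 |
| Power 99% | 38 |
| Two-sided equivalence (normal approximation) | 26 |
| SD multiplied by √2 | 44 |

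None comes near 100.

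**What would give about 100?** Changing one input and keeping the rest as stated, each of the following needs 86 per group (power 0.903), and 86/0.9 = 95.6, so 96 with dropout:

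- SD = 4.0
- margin = 1.0
- d = 1.0

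All three halve the ratio (M − d)/SD from 1.0 to 0.5, which is why they give the same answer. The values for exactly 90% power are:

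| Input changed | 90 evaluable per group | 100 evaluable per group |
|---|---|---|
| True nurse-arm deficit | 1.03 | 1.08 |
| SD | 4.12 | 4.34 |
| Margin | 0.97 | 0.92 |

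These values are back-solved. Nothing in the documents supports one over another.

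**Sensitivity to the unstated deficit** (M = 2.0, SD = 2.0, before dropout):

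| Deficit d | 0 | 0.5 | 0.75 | 1.0 | 1.25 |
|---|---|---|---|---|---|
| n per group | 23 | 39 | 55 | 86 | 151 |

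**The case against.** The best defence accepts the arithmetic and disputes what it means. Zero true difference is a convention that the plan never adopts. If the sponsor assumed a deficit near 1.0 point, the printed figures roughly agree (86 per group, 96 with dropout), and power is 0.916 at 90 and 0.940 at 100 evaluable per group. The defect is then an omitted input, not a wrong sum. Combinations can also work: alpha halved for two visits together with a deficit of 1.0 gives 101 per group. The margin of 2.0 is stated plainly, is contradicted nowhere, and stands in a subsection directly under the decision rule, so a reader would naturally apply it. On the printed inputs the trial has too many patients for ESS, not too few.

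Much of this stands. The margin is only one of several candidates for the error, an undisclosed deficit is a real possibility, and no loss of power on ESS has been shown. It does not rescue the sentence as written. Each route to 100 needs a value that the plan does not state or a change to one that it does. An assumption that moves the required size from 23 to 151 as it goes from 0 to 1.25 points cannot be left for the reader to guess. Nor can the size be attributed to quality of life, since section 2.7.1 says it was based on ESS.

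**Conclusion.** The concern holds. As written, section 2.7.1 claims that 100 per group were required for 90% power, and its own inputs do not give that figure. With a true difference of zero they need 23 per group (26 with dropout), so the stated size is about four times too large for the stated power, and the power at that size is above 99.99%. The factor of four rests on the zero-difference assumption. What does not rest on it is that the calculation cannot be reproduced from what is printed: either the margin, SD, power or sample size is wrong, or at least one input is missing. Which of these applies cannot be settled from the documents. The finding does not show that the trial is underpowered on ESS. It should be corrected before the analysis because the only statement of the ESS margin sits inside the calculation that does not close.

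**What to change.** Keep the 200 patients. Go back to the sponsor's own calculation and restate section 2.7.1 with the margin, SD, assumed true difference, alpha, power, and whether 100 is before or after the 10% dropout, so that the figures agree. Do not select an SD, margin or deficit merely because it returns 200.

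- If all the printed inputs are right and the true difference was zero, say that 200 exceeds what ESS needs and that power is above 99%.
- If a non-zero true difference was used, state it.
- If the margin used was not 2.0, correct it and apply that margin in the section 2.7 decision rule.

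The cost is wording, with no extra patients. The restated figures may look less favourable, and if the margin was misreported the decision threshold becomes stricter.

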2.8 Study timeline

February 2018- June 2018	Patient enrollment
September 2018	Primary completion
December 2018	Study completion

3. FUNDING

The clinical nurse will work part-time on this project over an anticipated period of one year. Taking into account her hourly salary including social security contributions, the budget for this project is 31 860 \$. These fees will be covered by the Sleep Apnea Research and Teaching Fund of the IUCPQ_UL Fondation & Alphonse L'Espérance Funds.

